6.3 Variables Recorded

- Past medical history
- Demographic data
- Smoking history
- Occupational history
- Current medications
- Laboratory data (complete blood count, electrolytes, creatinine, coagulation profile if available, results of fungal serologies if available)
- Chest CT characteristics:
 - Location of the nodule (lobe and segment)
 - Nodule size (longest axis)
 - Distance to the nearest visible bronchus on either CT plane (axial, coronal or sagittal)
 - Bronchus sign (airway aligned with nodule)
 - Distance to the nearest parietal pleura
- PET scan characteristics (FDG uptake (SUV))
- Procedural characteristics:
 - Duration of procedure
 - Number and type of biopsies
 - Use of FluoroNav, and divergence in mm if used
 - Radiation exposure
 - Complications (pneumothorax, bleeding, others)
- Time to procedure (delay between decision to biopsy and procedure)
- Time from identification of nodule to treatment for malignant nodules
- Need for another biopsy modality
- Need for an additional staging procedure
- Follow-up data.

7. Safety Reporting of Adverse Events

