3.2 Aims and Objectives

In this study, we propose to study in a 1:1 randomized controlled trial the diagnostic accuracy of navigation bronchoscopy (NB) with F-Nav (SuperDimension iLogic 7.2 ENB platform and later (SuperDimension, Medtronic, Minneapolis, Minnesota, USA)) using a non-inferiority study design (primary endpoint) versus the current clinical standard of care: CT-guided biopsy. We will in addition compare: complications rate including rate of pneumothorax and clinically significant bleeding, need for hospitalization

CONFIDENTIAL

after procedure, time to procedure, duration of the procedure, need for additional nodule biopsy, need for additional procedure for staging, radiation exposure from fluoroscopy and CT, and need for F-Nav during navigation bronchoscopy (secondary endpoints). Follow up has been chosen to be pragmatically deliverable while allowing full assessment of key outcomes, including false negatives to provide a robust, clinically meaningful trial result.

4. Study Design

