4.2 Patient Inclusion and Exclusion Criteria

Inclusion criteria:

1. Patient is \geq 18 years of age at time of signing informed consent .
2. Patient is referred for biopsy of a single indeterminate pulmonary nodule, with the following characteristics regarding size, location, accessibility, and probability of malignancy:
 - a) Intermediate or high pre-test probability of malignancy as defined by a pre-test probability of malignancy between 10% and 100%, using a validated clinical prediction model, which is either:
 - i. The Brock model¹⁴ if no PET scan data are available, or
 - ii. The Herder model¹⁵ if PET-CT data are available.
 - b) Size between 10 and 30 mm (long diameter).
 - c) Location peripheral, here defined as occupying the middle or outer third lung zones.
 - d) Accessible via navigation bronchoscopy and also accessible via CT-guided biopsy (i.e. the nodule is clinically suited to equal access by either procedure), as confirmed by an independent interventional panel (see Section 4.5).

Note: Prior to randomization, the main purpose of this study-provided central review is to establish panel agreement with local expertise offered by the participating study site, that local management of a consented candidate patient at the site can be achieved by standard of care navigation

CONFIDENTIAL

bronchoscopy or equally achieved by standard of care CT-guided biopsy (with either procedure able to be performed at the local institution).

Exclusion criteria:

1. Patients with proximal nodules, as defined by nodules present in the proximal 1/3 of the lung by dedicated software analysis (described below) will not be eligible for the study.
2. Patients with multiple nodules requiring biopsy (patients may have other nodules not considered for biopsy).
3. Radiologically abnormal mediastinal or hilar lymph nodes requiring endobronchial ultrasound.
4. Patients for whom stereotactic body radiation therapy is planned even if biopsies show no evidence of malignancy.
5. Patients with contraindication to biopsy or deep sedation/general anesthesia.
6. Patients unable or unwilling to comply with study follow-up schedule.
7. Patients previously randomized to the study.
8. Patients unable to provide documented informed consent.
9. Patients who are nursing or pregnant as verified by an optional standard of care pregnancy test. (Testing required only if deemed clinically necessary by the patient's study physician.)

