The LungCloud™ allows each site's clinical study coordinator to manage patients that have to be added to the clinical study. Informed consent can be electronically acquired or added manually in the system. After informed consent has been obtained, the patient's de-identified data will be shared with the study primary site.

As part of the study, the subject's chest CT will be displayed in the clinical study review web-portal for analysis by the independent interventional panel consisting of (1) an interventional pulmonologist expert in navigation bronchoscopy and (2) an interventional radiologist expert in CT-guided biopsy. The lung nodule will be assessed for its location in the proximal, middle or outer third of the lung by an independent expert lung nodule physician using a validated software analysis. Nodules accessible by ultrasound guided TTNA, conventional bronchoscopy or linear EBUS will be excluded. Nodules located in the middle or distal third will be included. If

CONFIDENTIAL

the nodule is deemed amenable to both bronchoscopic and CT-guided biopsy approach, the patient will be randomized.

This assessment involving central review by the interventional panel is intended to occur within **3 business days** after informed consent is obtained. Subsequent randomization of eligible patients is anticipated in conjunction with confirmation of enrollment (as outlined below in Section 5), with initiation of navigation bronchoscopy or CT-guided biopsy to occur within 3 weeks (30 calendar days) after a site is notified of randomization. In the event that a CT scan cannot be uploaded to LungCloud™ expeditiously enough for adjudication to occur within the mandatory 3 day post-informed consent window, central adjudication will proceed using one or multiple representative axial CT slices uploaded to CRF 2 in the study REDCap database.

[figure not shown]
Exclusion criteria for accessibility via navigation bronchoscopy:

1. Nodules with an airway greater/equal to 3 cm away from the lung nodule
2. Nodules located in areas deemed unreachable by an expert interventional bronchoscopist

Exclusion criteria for accessibility via CT-guided biopsy:

1. All nodules for which a fissure would have to be crossed
2. All nodules for which a large bulla would have to be crossed
3. All nodules located in areas deemed unreachable by expert interventional radiologist

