4.10 Study Flow

See Procedural Flow Chart (Section 14), Screening Flow Chart (Section 15) and Study Assessment Table (Section 16).

5. Enrollment Procedures

The Vanderbilt-Ingram Cancer Center (VICC) Coordinating Center will coordinate enrollment in the study.

Prior to registration, a copy of the IRB approval at the site will be kept on file at the Vanderbilt-Ingram Cancer Center (VICC) Coordinating Center. Eligible participants will be entered on study centrally in OnCore at the VICC Coordinating Center.

All patients MUST be registered with the Vanderbilt-Ingram Cancer Center (VICC) prior to the start of study procedures such as tissue acquisition. Registration can only be conducted during the business hours of 8AM – 5PM Central Time, Monday through Friday.

CONFIDENTIAL

Enrollment Process:

Potential patients will be screened using the REDCap VERITAS e-Eligibility tool. Eligible patients will be approached by key study personnel either in person or via phone. Patients who agree to participate will provide signed research informed consent. This can be accomplished using a printed paper consent form which is then scanned and uploaded to VERITAS e-Eligibility upon completion, or electronically via the e-consent module embedded within VERITAS e-Eligibility, in which patients may sign research informed consent electronically (either in clinic or after the e-consent form is emailed to them following full informed consent discussion from key study personnel over the phone). Once signed research informed consent has been obtained, a record for the subject is created in the REDCap VERITAS database. Central adjudication are performed within three business days as described in section 4.5, with determinations entered into the VERITAS database. Once central adjudication is complete, the subject's e-eligibility CRF part 2 is completed indicating whether they are eligible for randomization after central adjudication. Eligible patients are then randomized via a randomization module embedded within the VERITAS database.

Note:

Upon satisfactory review of eligibility documents submitted, the Coordinating Center will approve enrollment and issue a subject ID number if one was not issued at screening. Once registration/enrollment confirmation from Coordinating Center is received, proceed with protocol procedures.

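### Time to procedure is listed as a between-arm comparison, but its clock starts at the decision to biopsy, before randomisation; this causes no bias in days but can cost precision

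*Combined protocol and SAP*

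**What the plan says.** **Comparison.** Section 3.2 opens its list of further outcomes with "We will in addition compare: complications rate including rate of pneumothorax" and continues with "after procedure, time to procedure, duration of the procedure, need for additional nodule biopsy". It labels the whole list secondary endpoints. The secondary endpoint lists in the synopsis and in Section 4.8 do not contain time to procedure.

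**Definition.** The only definition is an entry in the list of recorded variables in Section 6.3: "Time to procedure (delay between decision to biopsy and procedure". No analysis method is given for it, and nothing splits the interval at randomisation.

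**Sequence.** Under Section 4.2, "Patient is referred for biopsy of a single indeterminate pulmonary nodule" is an inclusion criterion. Section 5 then sets out consent and panel review ("Central adjudication are performed within three business days as described in section 4.5"), followed by completion of the second eligibility form. Only after that does it say "Eligible patients are then randomized via a randomization module embedded within the VERITAS database".

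**Scheduling window.** Section 4.5 times the procedure from a later point: "with initiation of navigation bronchoscopy or CT-guided biopsy to occur within 3 weeks (30 calendar days) after a site is notified of randomization". Section 5 also counts from notification of randomisation.

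**The concern.** A between-arm comparison of waiting time should measure the wait that the assigned procedure can affect, and that wait begins at randomisation. The interval from the decision to biopsy to randomisation is a baseline quantity: it has the same distribution in both arms in expectation, and allocation cannot alter it. Including it adds variance and no signal.

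Two things are at stake. A real difference in waiting time between bronchoscopy and CT-guided biopsy is harder to detect. The delay reported for each pathway also contains consent and adjudication steps that belong to the trial and not to the pathway.

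**Working it through.** **Does the clock start before randomisation?** The decision to biopsy is not dated or defined. The order is inferred: referral for biopsy is an entry criterion (4.2), consent and panel review follow (4.5, 5), and randomisation comes last (5). No other order fits this text.

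**Inputs from the documents.** 112 per arm, from Section 6.1. It reproduces as the primary-endpoint sample size: with 90% in both arms, a margin of 0.10 and one-sided 5%, SE = sqrt(2 × 0.9 × 0.1 / 112) = 0.0401, and power = Φ(0.10/0.0401 − 1.645) = 80.2%. It is used here only as the number per arm. The documents give no mean, SD or expected difference for time to procedure.

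**Assumed inputs.** Post-randomisation SD s1 = 8 days; for scale, a uniform spread over 30 calendar days has SD 30/sqrt(12) = 8.7. Pre-randomisation SD s0 = 2, 5, 10 or 20 days, independent of the later wait. True difference 4 days, two-sided 5%, normal approximation.

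**Formulas.**
- Total SD = sqrt(s0² + s1²)
- Effective n per arm = 112 × s1² / (s0² + s1²)
- Difference detectable with 80% power = (1.96 + 0.84) × SD × sqrt(2/112)
- Power for 4 days = Φ(4 / (SD × sqrt(2/112)) − 1.96)

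| s0 (days) | Variance | SD | Variance ratio | Effective n per arm | Detectable difference (days) | Power for 4 days |
|---|---|---|---|---|---|---|
| 0 (clock at randomisation) | 64 | 8.0 | 1.0 | 112 | 3.0 | 96% |
| 2 | 68 | 8.2 | 1.06 | 105 | 3.1 | 95% |
| 5 | 89 | 9.4 | 1.4 | 81 | 3.5 | 89% |
| 10 | 164 | 12.8 | 2.6 | 44 | 4.8 | 65% |
| 20 | 464 | 21.5 | 7.3 | 15 | 8.1 | 28% |

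**Same question by ratio of SDs.** Take the difference that has 80% power on the post-randomisation wait alone. With s0/s1 of 0.5, 1 and 2, the standardised effect is multiplied by 1/sqrt(1 + (s0/s1)²) = 0.89, 0.71 and 0.45, and power falls to 71%, 51% and 24%.

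**Bias check.** In a simulation with mean waits of 14 and 17 days and a pre-randomisation interval of the same distribution in both arms, the mean difference was 3.0 days with either clock. Its standard error rose from 1.04 to 1.39. On a ratio scale the effect shrinks: 17/14 = 1.21 becomes 24/21 = 1.14 with 7 shared days, and 31/28 = 1.11 with 14.

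**Share due to the trial's own review.** If panel review were spread uniformly over 0 to 5 calendar days (3 business days plus a weekend, an assumption), its variance would be 25/12 = 2.1 and its SD 1.4 days. That adds 2.1/64 = 3% to the variance. A review of constant length adds none. A large loss needs wide variation between referral and consent, which the documents neither describe nor limit.

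**The case against.** The strongest reply is that this is a recorded variable and not an analysis specification. Both formal endpoint lists omit it, no test or model is attached to it, and the preferred interval could be derived later from dates already held. This stands in part: it limits the weight of the point, and the inconsistent status needs resolving in its own right. But Section 3.2 does commit to the comparison, and Section 6.3 holds its only definition.

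A second reply is that the loss may be trivial. This also stands. Section 16 puts consent, eligibility and radiology review under one visit, so a short and uniform pre-randomisation interval is compatible with the documents. With an SD of 2 days, nothing of note is lost.

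A third is that the delay from decision to procedure is what the patient experiences. That is a good reason to report it, but not to use it as the only basis for comparing arms.

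A reader might also infer stronger points that the documents do not support:
- *That the comparison is biased.* The pre-randomisation part is balanced in expectation, so the mean difference in days is unaffected.
- *That the trial's own review step is the main source of the loss.* Its contribution to the variance is small, as shown above.
- *That the different start of the scheduling window is a contradiction.* Section 5 explains the window as a safeguard against an overly delayed procedure, and a safeguard may use a different starting point from a delay measure.
- *That "Time from identification of nodule to treatment for malignant nodules" has the same fault.* Section 6.3 only records it, and no list names it as a between-arm comparison.

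**Conclusion.** The point holds as a minor, free improvement. If time to procedure is compared as Section 3.2 says and as Section 6.3 defines it, the interval includes a baseline stretch that allocation cannot affect. The unadjusted difference in days is unbiased but can be less precise, and the absolute delays include consent and adjudication time.

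The documents do not fix the size of the loss. Under the stated assumptions, power for a 4-day difference lies anywhere between 95% and 28%, against 96% with the clock at randomisation. The low end depends on a 20-day pre-randomisation SD for which the documents give no support. The result also rests on independence of the two intervals, and on the inference that the decision to biopsy precedes randomisation. The primary endpoint is not affected.

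**What to change.** - In Sections 3.2 and 6.3, define time to procedure for the between-arm comparison as days from the REDCap randomisation date to the start of the study procedure. Alternatively, keep the present clock and adjust for the decision-to-randomisation interval.
- Keep decision-to-procedure time as a descriptive variable, and state that it includes consent and central review.
- Reconcile the endpoint's status: either add time to procedure to the lists in the synopsis and Section 4.8, or remove it from the secondary endpoints in Section 3.2.

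The cost is a few lines of wording. Randomisation runs inside the study database and time to procedure is already recorded, so no new data collection should be needed.

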7.1 Grading

Adverse events will be graded according to the NCI's Common Terminology Criteria for Adverse Events (NCI CTCAE), Version 5.0, dated November 27, 2017, currently locatable via the following URL:
https://ctep.cancer.gov/protocoldevelopment/electronic_applications/docs/CTCAE_v5_Quick_Reference_8.5x_11.pdf

CONFIDENTIAL

If events are not listed in the CTCAE, severity may be designated as mild, moderate, severe, life-threatening, or fatal which respectively correspond to Grades 1, 2, 3, 4, and 5 on the NCI CTCAE, with the following definitions:

- **Mild:** Asymptomatic or mild symptoms; clinical or diagnostic observations only; intervention not indicated;
- **Moderate:** Minimal, local or noninvasive intervention indicated; limiting age-appropriate instrumental activities of daily living (ADL) such as preparing meals, shopping for groceries or clothes, using the telephone, managing money, etc;
- **Severe:** Medically significant but not immediately life-threatening; hospitalization or prolongation of hospitalization indicated; disabling; limiting self care ADL such as bathing, dressing and undressing, feeding self, using the toilet, taking medications;
- **Life-threatening:** Urgent intervention indicated to prevent risk of death present at the time of the event;
- **Fatal:** An event that results in the death of the patient.

Information on adverse events, whether serious or not, whether reported by the participant, directly observed, or detected by physical examination, laboratory test or other means, will be collected, recorded, followed and reported as described in the following sections.

7.2 Reporting Period

The procedures being performed, bronchoscopy and CT-guided biopsy, are standard of care for management of indeterminate pulmonary nodules. Therefore, collection of data regarding adverse events and serious adverse events will be limited in this study:

- Any serious or non-serious adverse event related to research procedures (i.e. the consent process, HIPAA compliance, etc.) will be collected.
- After informed consent but prior to initiation of navigation bronchoscopy or CT-guided biopsy, serious and non-serious adverse events should be reported only if possibly, probably or definitely attributed by the patient's study physician to a protocol-mandated research procedure or intervention.
- The principal AE reporting period will be within 7 days of the study procedure, as it would be exceedingly uncommon for a new biopsy-related complication to occur more than 7 days after the biopsy procedure. Effort should be made on post-procedure day #7 to assess for any complications which have not already risen to investigator awareness.
- Any serious adverse event that occurs \leq 7 days after initiation of navigation bronchoscopy or CT-guided biopsy, regardless of causality to participation in the study, must be reported to the Coordinating Center in an expedited fashion as directed below (Reporting Procedures).

CONFIDENTIAL

During the 7-day reporting period, non-serious adverse events should only be recorded if, in the opinion of the investigator, there is a reasonable possibility the event is attributable to participation in the study. Non-serious adverse events related to navigation bronchoscopy or CT-guided biopsy or the next phase of the patient's treatment or management should NOT be recorded.

Participants should be instructed to report any serious post-study event(s) that might reasonably be related to participation in this study. The investigator should notify the IRB and the Coordinating Center of any unanticipated death or adverse event occurring after a participant has discontinued or terminated study participation that may reasonably be related to the study.

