4.8 Outcomes

Primary endpoint

The primary endpoint will be diagnostic accuracy, as defined by the rate of technically successful biopsies leading to a definitive diagnosis, comparing the navigation bronchoscopy to the CT-guided biopsy pathway. Definitive diagnoses are pre-defined as any of the following:

- Malignancy on histological samples, **OR**
- Biopsies with abnormal tissue (excluding normal or absence of lung parenchyma) that are followed by a surgical lung biopsy yielding the same histological diagnosis, **OR**
- Specific benign histopathologic finding which accounts for the presence of a lung nodule (specifically including organizing pneumonia, frank purulence, granulomatous inflammation, or other specific benign finding) **AND**
- Absence of malignancy (true negative) over 1 year of longitudinal CT follow-up, defined as:
 - the nodule markedly regresses or resolves on follow-up imaging, **OR**
 - a persistent nodule has not been diagnosed as malignant, **AND**
 - there are no plans for repeat invasive diagnostic procedures through 12 months follow-up.

Biopsies with normal or absence of lung parenchyma, atypia or mild inflammation will be considered non-diagnostic. All diagnoses (from both arms) will be determined by a blinded, independent, expert lung pathologist (i.e. blind to the biopsy technique) and all non-diagnostic biopsy specimens will be reviewed by an independent expert pathologist.

Linear EBUS for lymph node interrogation and staging will be performed in the same procedure after the navigation bronchoscopy for staging purposes as per standard of care.

Secondary endpoints

- Rate of pneumothorax
- Rate of pneumothorax requiring chest tube placement
- Clinically significant bleeding (defined by bleeding requiring intervention)
- Need for hospitalization after procedure
- Duration of the procedure (from bronchoscope in to bronchoscope out for the bronchoscopy arm and from first needle in to last needle out for CT-guided biopsy)
- Procedural factors associated with improved yield (type of biopsy, number of biopsies, use of radial ultrasound, presence of a bronchus sign, biopsy site)
- Need for additional nodule biopsy
- Need for additional procedure for staging

CONFIDENTIAL

- Radiation exposure from fluoroscopy-guided bronchoscopy and CT for CT-guided biopsy
- Need for F-Nav during navigation bronchoscopy
- Adequacy of specimens collected for molecular testing when needed.

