7.6.2 Serious Adverse Event (SAE)

A serious adverse event is an undesirable sign, symptom or medical condition which:

- Is fatal or life-threatening;
- Requires or prolongs inpatient hospitalization;
- Results in persistent or significant disability/incapacity;
- Constitutes a congenital anomaly or birth defect; or
- Jeopardizes the participant and requires medical or surgical intervention to prevent one of the outcomes listed above.

Events **not** considered to be serious adverse events are hospitalizations for:

- Routine treatment or monitoring of the studied indication, not associated with any deterioration in condition, or for elective procedures.
- Elective or pre-planned treatment for a pre-existing condition that did not worsen.
- Emergency outpatient treatment for an event not fulfilling the serious criteria outlined above and not resulting in inpatient admission.

CONFIDENTIAL

- Respite care.

7.6.3 *Expectedness*

Expected: Expected adverse events are those that have been previously identified as resulting from administration of the agent. For the purposes of this study, an adverse event is considered expected when it appears in the study protocol or current adverse event list, in applicable information describing use of a marketed product in the standard of care setting (e.g. product manual, investigator's brochure, package insert) or is included in the informed consent document as a potential risk.

Unexpected: An adverse event is considered unexpected when it varies in nature, intensity or frequency from information provided in the study protocol or current adverse event list, in applicable information describing use of a marketed product in the standard of care setting (e.g. product manual, investigator's brochure, package insert) or when it is not included in the informed consent document as a potential risk.

7.6.4 *Attribution*

Attribution is the relationship between an adverse event or serious adverse event and participation in the study. Attribution will be assigned as follows:

- Definite – The AE is clearly related to study participation.
- Probable – The AE is likely related to study participation.
- Possible – The AE may be related to study participation.
- Unlikely – The AE is doubtfully related to study participation.
- Unrelated – The AE is clearly NOT related to study participation.

7.7 **Reporting Procedures**

7.7.1 *General Considerations*

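### Section 7.2, as worded, bars recording non-serious biopsy complications that 3.2, 4.8, 6.3 and its own day-7 check expect to be collected

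*Combined protocol and SAP*

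**What the plan says.** Section 7.2 opens by noting that both procedures are standard of care and that "collection of data regarding adverse events and serious adverse events will be limited in this study". Within that limit it requires every serious adverse event up to 7 days after the procedure to be reported, whatever its cause. A non-serious event is to be recorded only if the investigator thinks it may be due to study participation. It then adds: "Non-serious adverse events related to navigation bronchoscopy or CT-guided biopsy or the next phase of the patient's treatment or management should NOT be recorded".

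Other places point the other way:

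- 7.2 itself, on follow-up: "Effort should be made on post-procedure day #7 to assess for any complications which have not already risen to investigator awareness".
- 6.3, under procedural characteristics: "Complications (pneumothorax, bleeding, others".
- 3.2, on what the arms will be compared for: "complications rate including rate of pneumothorax and clinically significant bleeding".
- 4.8 lists as secondary endpoints any pneumothorax, pneumothorax needing a chest tube, hospitalization after the procedure, and "Clinically significant bleeding (defined by bleeding requiring intervention".

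Section 7.1 says that information on adverse events, serious or not, "will be collected, recorded, followed and reported as described in the following sections", which hands control to 7.2. The assessment table in section 16 marks adverse events at every visit.

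**The concern.** A site that follows 7.2 to the letter leaves out a non-serious complication of either biopsy. A site that follows 6.3 enters it. Both can claim to be complying. When the data are analysed, an empty entry under other complications could then mean that nothing happened or that the event was deliberately not written down, and the analyst could not tell which. An event that was never recorded cannot be recovered by tabulating by arm.

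This matters because the comparative safety picture is part of the case for the trial. Section 4.1 justifies the non-inferiority design partly by an expected reduction in complications with bronchoscopy. A descriptive account of all procedural complications, in both arms, is what a reader would want beside the accuracy result.

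**Working it through.** The plan gives no figure on this point, so the check is a comparison of texts followed by a count of what is exposed.

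**Step 1. Is a biopsy complication an adverse event here?** Yes. Section 7.6.1 covers any undesirable sign, symptom or condition that appears or worsens after a procedure specified in the protocol, related or not. The protocol therefore draws no line between adverse events and complications that would take the 6.3 variable outside 7.2.

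**Step 2. Does 7.2 restrict recording or only reporting?** Its words concern recording, and its opening concerns collection of data. Section 7.1 also speaks of collecting and recording. No sentence confines the restriction to the AE form or to expedited reports.

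**Step 3. Literal 7.2 against the other places.**

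| Place | What it expects | Literal 7.2 |
|---|---|---|
| 4.8 | Any pneumothorax, including non-serious cases | Barred |
| 6.3 | Pneumothorax, bleeding and other complications | Non-serious ones barred |
| 3.2 | A complications rate, with pneumothorax and bleeding as included items | Non-serious part barred |
| 7.2, day 7 | A search for complications, with no limit to serious ones | Non-serious findings may not be recorded |

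The first row shows that the literal rule cannot be what was meant: it would remove part of a named endpoint.

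**Step 4. What is collected by another route?** The 4.8 endpoints must be collected because they are endpoints. Serious events to day 7 are reported under 7.2, and 7.6.2 includes an event that "Jeopardizes the participant and requires medical or surgical intervention to prevent one of the outcomes listed above".

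**Step 5. What remains?** Non-serious complications with no named endpoint. Apart from minor bleeding, which 6.3 names, they rest on the single word for other complications in 6.3. The risks in 7.3 give an idea of the kinds involved.

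- Bronchoscopy: 10 types in its own list, plus pain from the general list for both procedures, gives 10 + 1 = 11. Remove pneumothorax and bleeding (4.8) and heart attack (assumed always serious): 11 − 3 = 8.
- CT-guided biopsy: 5 types plus pain gives 5 + 1 = 6. Remove pneumothorax and bleeding: 6 − 2 = 4.
- The 4 CT types (pain, breathing difficulty, infection, low oxygen) are all among the 8. The other 8 − 4 = 4 are vocal cord spasm, bronchial spasm, vomiting and dizziness.

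These are counts of types, not of patients or events, and the lists are not presented as exhaustive. Bleeding that needs no intervention is not counted here, although it also falls outside the 4.8 definition.

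**Step 6. Can the loss be sized?** No. The documents give no rate for these non-serious events in either arm, and do not show how sites read 7.2 or how the case report form is laid out.

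**The case against.** The strongest reply is that the literal reading proves too much. If 4.8 keeps pneumothorax alive despite 7.2, then 6.3, which lists pneumothorax, bleeding and other complications as one variable, should keep the rest alive too. Context supports this. Section 7 is about safety reporting and 6.3 is about study variables. The sentence just before the disputed one ties recording to study participation, and 7.6.4 defines attribution in those terms. On that view 7.2 only says that harm from a standard-of-care procedure is not a research adverse event. Section 6.2 gives similar reasoning when it explains why there is no interim safety analysis. The day-7 check can be read as a search for reportable events. No overall complication rate is defined in 4.8, so no planned endpoint needs the residual category. More consequential events leave other traces: 7.3 has the procedure aborted for low oxygen or ECG changes, and 4.6 and 4.7 class a procedure as non-diagnostic if a complication prevents biopsy.

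Most of this stands. The narrow reading is probably the intended one, the events at issue are mostly minor, and the case report forms, which might settle the matter, are not in the documents. It does not make the sentence harmless. A named endpoint is an obligation no site would overlook; a residual word in a variable list is much weaker against an emphatic instruction not to record. The protocol states no order of precedence between them. A sentence that must be read against its own words to save an endpoint should be corrected.

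A reader might go further and infer that the loss would fall mainly on bronchoscopy and flatter it: its risk list is longer, 7.3 puts its greatest risks in sedation and handling of the scope, and only that arm requires general anesthesia. The documents do not support this. The rule applies equally to both arms, four of the exposed types are common to both, 7.3 describes the listed bronchoscopy risks as very rare, and there are no rates from which a direction could be derived.

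**Conclusion.** The inconsistency is real and should be corrected, but its reach is limited. As worded, 7.2 forbids recording that 3.2, 4.8, 6.3 and the day-7 check presuppose. In practice the exposure is confined to non-serious complications without a named endpoint, in both arms. Neither the size nor the direction of any loss can be computed, and it may be nil if every site already reads 7.2 narrowly.

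A reader might also infer that the pneumothorax, chest-tube, bleeding or hospitalization endpoints are compromised. They are not: 4.8 requires them. The primary endpoint, sample size and non-inferiority margin are untouched.

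The conclusion assumes that no instruction outside these documents, such as a form-completion guide, already resolves the conflict. The scope count further assumes that heart attack is always serious.

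**What to change.** Replace the disputed sentence in 7.2 with text such as:

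> Non-serious events caused by either biopsy procedure are not entered on the AE form and need no expedited report. Complications of either biopsy, serious or not, are nevertheless recorded in both arms in the procedural complication field (6.3) through the day-7 contact. Non-serious events arising from the next phase of treatment are not recorded.

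Report these complications descriptively by arm. No new composite endpoint is needed. A CTCAE grade could be added, since 7.1 already adopts version 5.0, but it is optional and not needed to resolve the conflict.

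The cost is one amended sentence and slightly more data entry. The complication field is in 6.3 and the day-7 contact is already scheduled in section 16. Data for patients treated before the change may be incomplete for these events and should be labelled so in any table.
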